Therefore, we propose to perform a prospective randomized pilot clinical trial, stratified by primary tumor site, to evaluate the degree of xerostomia and quality of life (QOL) in subjects with HN-SQCC treated with radiation therapy under margin-based and robust radiotherapy treatment plans. Margin-based plans will use both biological (biological optimization) and physical objectives whereas robust planning will use physical objectives for sparing of the parotid glands. Intensity-modulated radiation therapy (IMRT) and standard chemotherapy will be used. QOL (quality of life) will be measured using the EORTC QLQ-C30 questionnaire and EORTC QLQ-H&N35 (head and neck) module before radiotherapy (baseline) and then 3, 6, 9 and 12 months after radiotherapy. Xerostomia will be measured in study subjects using two patient-reported scoring systems completed by each subject before radiotherapy and then 3, 6, 9, and 12 months after radiotherapy: the LENT/SOMA grading system and the University of Michigan's Xerostomia Questionnaire (XQ; see Eisbruch *et al.* 2001). The data collected by this randomized pilot clinical trial will be used to inform the design of, and decision-making for, future larger studies that seek to compare different methods of radiotherapy planning in the treatment of HN-SQCC.

STUDY OBJECTIVES

Primary Objective

To evaluate descriptively over time the prevalence and grade of xerostomia in subjects treated for HN-SQCC with IMRT under either biologically optimized margin-based or robust photon radiotherapy.

Secondary Objectives

- 1) To compare descriptively the arm treated with IMRT under the margin-based radiotherapy plan to the arm treated with IMRT under the robust radiotherapy plan for possible differences in derived outcomes of interest, including but not limited to: (1) occurrence rate of grade ≥ 2 xerostomia as determined using the LENT/SOMA scale; and (2) occurrence rate of overall score ≥ 30 on the XQ.
- 2) To obtain NTCP values of the parotid glands from both margin-based and robust radiotherapy treatment plans using validated parameter values of the NTCP mean dose model. Each subject will have their parotid NTCP values computed under both plans, even though they will receive IMRT delivered under only the plan they are randomized to.
- 3) To obtain dose statistics for dose delivered to the parotid glands of each subject via either margin-based or robust treatment plans.

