- Subject becomes pregnant (pregnancy to be reported along same timelines as a serious adverse event).

The Principal Investigator will be notified, and treating physician will document the reason for study removal and the date the subject was removed in the subject's medical record. The study coordinator will record the reason for removal and date in the Case Report Form (CRF).

STUDY PROCEDURES

Investigator will use one of the two strategies (i.e. Margin based or Robust) to plan for radio-therapy. Both of the strategies are standardly used at UAMS. Generally, it is just a physician's preference that determines which is used.

Margin-based and robust radiotherapy are both standard ways of delivering radiotherapy; therefore, no protocol-specific procedures are required with the chemo-radiotherapy.

The EORTC questionnaires and the xerostomia assessments will be filled out at 3, 6, 9 and 12 months after chemo-radiotherapy.

Radiotherapy

Subject will receive either routine margin-based or robust radiotherapy. The selection of which type of planning will be assigned to a subject will be determined in a 1:1 randomized fashion with stratification by primary tumor site.

Follow-up visits

Subjects will be seen in Radiation Oncology every 3 months for one year. Adverse events will be assessed during routine physical exams at each visit. In addition, at the time of each visit the subject will complete the EORTC quality of life-30 questionnaire and associated module HN-35 module, and subjective LENT/SOMA xerostomia scoring form.

MEASURES

Xerostomia: The Late Effects of Normal Tissues Subjective-Objective Management Analytic (LENT-SOMA) system includes subjective (patient-rated) and objective (clinician-rated) indices of radiotherapy toxicities [23]. The patient-rated xerostomia item is used in the current study. The item is rated on a 4-point Likert scale with 1 being the minimum and 4 being the maximum grades shown on the form. Evidence supports the convergent and construct validity of this measure [22, 23]. The University of Michigan's Xerostomia Questionnaire (XQ) is a brief, 8-item measure of patient-reported xerostomia. Individual items are rated on a 10-point scale with 0 being the minimum and 10 being the maximum on each item. The instrument has demonstrated evidence of internal consistency, test-retest reliability, construct validity, and sensitivity to change [24-26].

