This study also has the following secondary objectives:

- 1) To compare descriptively the arm treated with IMRT under the margin-based radiotherapy plan to the arm treated with IMRT under the robust radiotherapy plan for possible differences in derived outcomes of interest, including but not limited to: (1) occurrence rate of grade ≥ 2 xerostomia as determined using the LENT/SOMA scale; and (2) occurrence rate of overall score ≥ 30 on the XQ.
- 2) To obtain NTCP values of the parotid glands from both margin-based and robust radiotherapy treatment plans using validated parameter values of the NTCP mean dose model. Each subject will have their parotid NTCP values computed under both plans, even though they will receive IMRT delivered under only the plan they are randomized to.
- 3) To obtain dose statistics for dose delivered to the parotid glands from both margin-based and robust treatment plans.
- 4) To determine quality of life (QoL) at baseline and at 3, 6, 9 and 12 months after treatment using the EORTC QLQ-C30 instrument combined with the EORTC QLQ-H&N35 module. The main scores of interest at each time point will be the global QoL scale and the individual scales for dry mouth, oral pain, swallowing, opening mouth, sticky saliva, and social eating.
- 5) To correlate NTCP values with change in QoL results.

To accomplish this study's secondary objectives, the analysis will proceed as follows:

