number and proportion of subjects whose answer falls into each ordered category. Data will be graphed using box plots or scatter plots versus treatment arm and profile plots versus time point. In general, the mean differences between treatment arms will be estimated at each time point, and such estimates will be accompanied by two-sided 90% confidence intervals. Exploratory mixed-models analysis may be used in follow-up mode, as time permits, to explore more deeply the differences between treatment arms and how they change over time.

- 5) Changes in QoL results after treatment (compared to baseline) will be calculated at each post-treatment time point, then assessed for correlation with NTCP values by Spearman correlation analysis.

For analyses in support of the secondary objectives, the outcomes at all time points will be of interest, but outcomes at the 12-month time point will be of special interest because of this time point's prominence in previous studies such as PARSPORT [22].

Sample-size considerations. We plan to consent up to 75 subjects in order to reach our maximum accrual of 50 subjects. Twenty-five subjects will be assigned randomly to IMRT under the margin-based radiotherapy plan, and 25 subjects will be assigned randomly to IMRT under the robust radiotherapy plan.

The IMRT arm of the PARSPORT study [22] lost 17% of its enrolled subjects to death and dropout before they could be evaluated at 12 months for that study's primary endpoint, grade ≥ 2 xerostomia. If similar results hold in our study, and if we enroll 25 subjects per treatment arm, then we can expect the number of subjects who remain on each treatment arm for 12 months to be binomially distributed with expected value of 20.75 and 95% probability of being 18 or higher.

In each analysis, the precision of the estimates can be quantified through their standard errors, with smaller standard errors denoting greater precision. At 3 months, when each treatment arm should still contain 25 subjects, the standard

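### For quality of life, the only committed arm comparison is one visit at a time; a supplementary four-visit average difference would be more precise at almost no cost, but none is specified

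*Combined protocol and SAP*

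**What the plan says.** Secondary objective 4 reads "To determine quality of life (QoL) at baseline and at 3, 6, 9 and 12 months after treatment". The instruments are the EORTC QLQ-C30 and the H&N35 module. Seven scores are named as the main ones: global quality of life, dry mouth, oral pain, swallowing, opening mouth, sticky saliva and social eating.

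Item 4 of the secondary analyses in the Statistical Considerations summarizes these by arm and time point. For the arm comparison it states as a general rule: "the mean differences between treatment arms will be estimated at each time point, and such estimates will be accompanied by two-sided 90% confidence intervals". It then adds: "Exploratory mixed-models analysis may be used in follow-up mode, as time permits", with the stated purpose "to explore more deeply the differences between treatment arms and how they change over time". It gives no model form, covariance structure, baseline adjustment or contrast.

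The closing paragraph on the secondary objectives says that all time points matter but that "outcomes at the 12-month time point will be of special interest".

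The sample size (25 per arm) is justified by precision alone. The quoted standard errors are for one arm at one visit. Under Radiotherapy, allocation is "determined in a 1:1 randomized fashion with stratification by primary tumor site".

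**The concern.** Each subject can contribute four post-treatment scores on each of seven scales. The committed analysis turns these into 7 × 4 = 28 separate post-treatment arm differences, each with its own 90% interval. None of the 28 combines a subject's visits, so within-subject variation between visits is not averaged down. A subject scored at 3, 6 and 9 months but lost before 12 adds nothing to the 12-month difference.

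The only analysis that could combine visits depends on spare time, and its output is left open. If it is run, the model and contrast would be chosen after the data are seen, across seven scales. That makes any overall difference harder to interpret. The plan commits more firmly for the xerostomia measures, where it says mixed models will be used, though still as exploratory work.

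What is at stake is how much the pilot's quality-of-life data can tell the designer of a larger trial. The validity of the pilot is not in question.

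**Working it through.** **Inputs from the Sample-size considerations.** 25 per arm; 17% lost by 12 months, so 25 × 0.83 = 20.75 expected per arm; as few as 18 per arm at 12 months.

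**Inputs assumed.** Equal SDs across visits and arms. Between-visit correlation ρ of 0.4 to 0.8, with 0.9 as a stress case. Loss spread evenly after 3 months.

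**Step 1: the plan's own figures.** SE of a mean = SD/√n: 1/√25 = 0.200 and 1/√18 = 0.236. The binomial probability of 18 or more out of 25 at 0.83 is 0.950. These agree with the plan.

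**Step 2: SE of an arm difference at one visit**, SD × √(2/n).
- 3 months: √(2/25) = 0.283 SD.
- 12 months, expected number: √(2/20.75) = 0.310 SD.
- 12 months, 18 per arm: √(2/18) = 0.333 SD.

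**Step 3: four-visit average, complete data.** Under compound symmetry the one-visit SE is multiplied by √((1 + 3ρ)/4): 0.742, 0.837, 0.922 and 0.962 at ρ = 0.4, 0.6, 0.8 and 0.9. At ρ = 0.6 with 25 per arm this gives 0.283 × 0.837 = 0.237 SD.

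**Step 4: the same with dropout.** Per arm, 83% have all four visits and 17%/3 ≈ 5.7% have exactly three, two or one. Expected numbers are 25, 23.6, 22.2 and 20.75. For each pattern, take the inverse correlation matrix of the observed visits, weight it by the number of subjects, sum, and invert to obtain V, the covariance matrix of the four visit means. With a = (¼, ¼, ¼, ¼), the SE of the average difference is √(2a′Va). The SE of the model-based 12-month difference is √(2V₄₄).

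| ρ (compound symmetry) | SE of average | vs 12 months (0.310) | vs 3 months (0.283) | Model-based 12-month SE | vs 0.310 |
|---|---|---|---|---|---|
| 0.4 | 0.215 | 31% smaller | 24% smaller | 0.305 | 2% smaller |
| 0.6 | 0.240 | 23% smaller | 15% smaller | 0.299 | 4% smaller |
| 0.8 | 0.263 | 15% smaller | 7% smaller | 0.291 | 6% smaller |
| 0.9 | 0.273 | 12% smaller | 3.5% smaller | 0.287 | 7.5% smaller |

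If correlation decays with time (AR(1), 0.4 to 0.8 between adjacent visits), the average gains 19 to 37% against 12 months, and the 12-month estimate itself gains 0.6 to 4%.

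**Step 5: on the interval scale** (z = 1.645). The 90% half-width is 1.645 × 0.310 = 0.51 SD at 12 months. For the average it is 1.645 × 0.215 = 0.35 SD at ρ = 0.4 and 1.645 × 0.263 = 0.43 SD at ρ = 0.8.

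None of these figures uses baseline score or tumor site as a covariate. The documents give nothing from which to size that further gain.

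**The case against.** The strongest reply is that the two intervals are for different quantities. Objective 4 asks about quality of life at each visit, and the plan singles out 12 months. By-visit differences answer that question directly; no objective asks for a four-visit average. A reader might take the 15 to 31% as precision lost on the plan's own 12-month target. The documents do not support that: for the 12-month difference, the repeated-measures model saves only about 2 to 6%, or 0.6 to 4% under AR(1). This objection stands, and it limits the point to a supplementary summary.

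Three further points also stand.
- A reader might infer that the visits will never be combined. The optional mixed model could do so. What can be said is that no such estimate is committed or specified.
- A reader might infer that the four-visit average is the most precise comparison the data allow. Nothing shows this; an unadjusted average leaves out the baseline score and the stratification factor.
- Variation between visits includes real change over time, which the plan intends to describe with profile plots. An average can hide it.

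The reply also notes that this is a descriptive pilot with no hypothesis test or power target, and that the plan judges its single-visit precision adequate. That removes any charge of error. It does not settle the matter, because the quoted standard errors are for one arm's estimate. The SE of an arm difference is √2 times larger, and the plan does not state it.

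**Conclusion.** The point holds as a modest gap in efficiency and pre-specification. The committed quality-of-life comparison is visit by visit, and the plan fixes no summary arm difference across the four post-treatment visits.

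Adding one would give a supplementary estimate with SE 0.215 to 0.263 SD, compared with 0.310 SD for a single 12-month comparison and 0.283 SD for a 3-month one. That rests on equal SDs, compound symmetry, even loss after 3 months and a correlation of 0.4 to 0.8 that the documents do not give. The size of the gain is sensitive to the correlation, and at 0.9 little remains against the 3-month visit.

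It would be wrong to read this as a flaw in by-visit estimation, or as a reason to replace the 12-month difference. The change is worth making because the sample size rests on precision, the data are already collected, and the plan already names this class of model.

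**What to change.** In item 4, replace the optional sentence with a commitment to one repeated-measures model for each of the seven listed scales. The terms are arm, visit and arm-by-visit, with baseline score and tumor site as covariates and a stated covariance structure. From each model report:
- the arm difference averaged over 3, 6, 9 and 12 months, with a two-sided 90% interval;
- the 12-month arm difference, with a two-sided 90% interval.

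Keep the planned by-visit summaries and differences beside these, and label the average as supplementary.

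State two limitations in the plan. An average over visits can dilute an effect that appears only late, which is why the 12-month estimate stays in the table. The model also assumes data are missing at random, and for subjects who die it implicitly carries quality of life past death. Since the 17% loss figure covers deaths as well as dropout, the numbers of each should be shown by arm and visit.

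The cost is some plan wording and seven model fits. No extra subjects, visits or questionnaires are needed.

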- 1) Xerostomia grades from the LENT/SOMA scale will be dichotomized as grade ≥ 2 versus grade < 2 , then summarized by treatment arm and time point as the number and proportion achieving grade ≥ 2 . The dichotomization is placed at grade $</\geq 2$ because that was the cutpoint used in the PARSPORT study [22], but we will also consider an alternative dichotomization at grade $</\geq 3$. As for the overall XQ score (a continuous variable), we will dichotomize it at different cutpoints chosen for their potential clinical relevance, beginning with a cutpoint of $</\geq 30$, then summarize the result by treatment arm and time point as the number and proportion of subjects who surpass the cutpoint. For all dichotomized versions of both xerostomia measures, the proportions on each arm and proportion differences between treatment arms will be estimated at each time point. Estimated proportions and their differences will be accompanied by two-sided 90% confidence intervals. Exploratory mixed-models analysis may be used in follow-up mode, as time permits, to explore more deeply the differences between treatment arms and how they change over time.
- 2) NTCP values from both plans will be summarized by plan and treatment arm as the mean, SD, median, quartiles, and range. Data will be graphed using box plots versus treatment arm. Plans will be compared descriptively by calculating the paired difference between them, and summarizing the result as means, SDs, and ranges. Means will be accompanied by 90% confidence limits.
- 3) Dose statistics on each subject (i.e., the mean, SD, median, 1st and 3rd quartiles, 5th percentile, and 95th percentile of dose received by the subject) will be summarized by statistic and treatment arm as the mean, SD, median, quartiles, and range. Data for each statistics will be graphed using box plots versus treatment arm.
- 4) The global EORTC QOL scale and individual scales for dry mouth, oral pain, swallowing, opening mouth, sticky saliva, and social eating will be summarized by treatment arm and time point as the mean, SD, and range, and also (for individual Likert-scaled items that have 5 or fewer ordered categories) as the

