errors on estimated means will be ± 0.200 times the group SDs, while the standard errors on proportion estimates of 10%, 30%, and 50% will be $\pm 6.0\%$, $\pm 9.2\%$, and 10.0%, respectively. At 12 months, when the number remaining on each treatment arm could be as few as 18 subjects, the standard errors on estimated means will be ± 0.236 times the group SDs, while the standard errors on proportion estimates of 10%, 30%, and 50% will be $\pm 7.1\%$, $\pm 10.8\%$, and $\pm 11.8\%$, respectively. These standard errors are considered small enough to assure that the estimates obtained from this pilot clinical trial will have the level of precision needed to be informative in the design of future larger studies that seek to compare different methods of radiotherapy planning in the treatment of HN-SQCC.

STUDY MANAGEMENT

Registration procedures

All subjects must be registered with the Cancer Clinical Trials Office before enrollment to study. Prior to registration, eligibility criteria must be confirmed with the Research Staff. To register a subject, call CCTO Monday through Friday, 8:00AM-4:30PM.

Randomization

Twenty-five subjects will be assigned randomly to IMRT under the margin-based radiotherapy plan, and 25 subjects will be assigned randomly to IMRT under the robust radiotherapy plan.

The study coordinator will use RPRS, a cancer Biomedical Informatics Grid (caBIG®, NCI) application, to randomize the subject to either the Margin-Based Arm or the Robust Arm. Once a subject is registered in RPRS, the computer system will generate a randomly assigned arm.

Data Handling and Record Keeping

Data must be submitted according to protocol requirements for ALL subjects registered, whether or not study procedures are performed. For screen failures, only the eligibility criteria case report form will be completed. Data obtained during the study will be collected at each subject visit and entered into the protocol database. Subjects will be registered in RPRS, a cancer Biomedical Informatics Grid (*caBIG*®, NCI) application. Data will be entered into OpenClinica through electronic web-based case report forms (CRFs). OpenClinica is a secure open source system for electronic data capture and clinical data management. All information in OpenClinica will be coded with a unique identifier and will be stored in the database indefinitely. In the event that a subject fails screening, only the eligibility criteria case report form will be completed.

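### The arm can be known before contouring and planning, so effort on the plan to be treated can bias the paired NTCP comparison; locking contours and both plans first would prevent that

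*Combined protocol and SAP*

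**What the plan says.** All places are in the combined protocol and SAP.

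- **Study Management, Randomization:** "Once a subject is registered in RPRS, the computer system will generate a randomly assigned arm". No planning milestone is attached to this step.
- **Study Management, Registration procedures:** "All subjects must be registered with the Cancer Clinical Trials Office before enrollment to study". Eligibility must be confirmed first. Contours and plans are not mentioned.
- **Study Procedures:** "Investigator will use one of the two strategies (i.e. Margin based or Robust) to plan for radio-therapy". On choice outside the trial: "Generally, it is just a physician's preference that determines which is used". On control of the treatment process: "no protocol-specific procedures are required with the chemo-radiotherapy".
- **Study Procedures, Radiotherapy:** "The selection of which type of planning will be assigned to a subject will be determined in a 1:1 randomized fashion", stratified by primary tumor site.
- **Secondary objective 2** (Study Objectives, repeated in Statistical Considerations): "Each subject will have their parotid NTCP values computed under both plans", although only the randomized plan is delivered.
- **Statistical Considerations, analysis of secondary objective 2:** "NTCP values from both plans will be summarized by plan and treatment arm". The two plans are then compared by the within-subject difference, with 90% limits on means.
- **Statistical Considerations, opening:** the trial is open-label.

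The document does not say when contours are drawn relative to randomization, who makes the two plans, whether that person knows the arm, or whether anything is fixed before the arm is released.

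**The concern.** The intervention is the radiotherapy plan itself. Contouring and optimisation are human steps that determine parotid dose and hence NTCP. If the arm is already known, one of a subject's two plans is known to be for treatment and the other only for calculation, so the effort spent on them may differ.

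Three results are exposed:

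1. The pooled paired NTCP difference, if the extra effort on the plan to be treated differs by method. The stated role of physician preference makes that plausible.
2. The NTCP summaries by plan and arm, even if the extra effort is equal.
3. The contours. If drawn with the arm known, they could differ by arm. That would affect dose and NTCP and, through delivered dose, possibly the xerostomia and quality-of-life summaries, and the analysis could not undo it.

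The pilot is meant to inform larger trials comparing planning methods, so a distorted difference between methods could carry into their design.

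**Working it through.** **The plan's own figures.** With 25 per arm and 17% loss, the expected number at 12 months is 25 × 0.83 = 20.75, and the exact binomial P(X ≥ 18) is 0.9505. Both match the text. The stated standard errors also reproduce: 1/√25 = 0.200 and 1/√18 = 0.236 times the SD; for proportions of 10%, 30% and 50%, they are 6.0%, 9.2% and 10.0% at n = 25 and 7.1%, 10.8% and 11.8% at n = 18. This point disputes none of them. The plan gives no figure for a planning bias or for the SD of paired NTCP differences, so both are assumed below.

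**Sequence.** The arm follows RPRS registration, and no milestone ties contouring or planning to either side of it. Knowledge of the arm during planning is therefore possible, but not stated.

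**Algebra.** Let D be NTCP under the robust plan minus NTCP under the margin plan, with 25 subjects per arm. Let extra effort lower the NTCP of the plan to be treated by bR points in the robust arm and bM points in the margin arm.

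- Robust arm: mean D shifts by −bR.
- Margin arm: mean D shifts by +bM.
- Pooled: (25 × (−bR) + 25 × bM)/50 = −(bR − bM)/2.
- Gap between the arms' mean D (margin arm minus robust arm): bM − (−bR) = bR + bM.
- Contrast of delivered plans between arms: −(bR − bM).

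In the summaries by plan and arm, the robust plan looks better by bR in the robust arm than in the margin arm. The margin plan looks better by bM in the margin arm than in the robust arm.

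**Scale.** Assume the SD of D is 5 NTCP points and use the normal quantile 1.645 for 90% limits.

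- Pooled mean, n = 50: 1.645 × 5/√50 = 1.16.
- Difference between arms of 25: 1.645 × 5 × √(2/25) = 2.33.

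Both are proportional to the SD. Halving it to 2.5 gives 0.58 and 1.16; doubling it to 10 gives 2.33 and 4.65.

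**Illustrations, in NTCP points (assumed).**

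| bR | bM | Pooled shift | Gap between arms |
|---|---|---|---|
| 1 | 1 | 0 | 2 |
| 3 | 3 | 0 | 6 |
| 3 | 1 | −1.0 | 4 |
| 3 | 0 | −1.5 | 3 |

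At an SD of 5, the pooled shift exceeds its half-width of 1.16 only in the last row. The gap exceeds 2.33 in every row but the first. Swapping bR and bM reverses the sign of the pooled shift. If both plans are finished before the arm exists, bR = bM = 0.

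**The case against.** The strongest reply is that the document does not put planning after assignment. Registration with the trials office and registration in RPRS may be separate steps, and RPRS registration might in practice come after planning. A reader might infer that the site knows the arm before it contours, but the text supports only that it can. This part of the objection stands.

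A reader might also infer that the paired comparison is certainly biased. It is not: under 1:1 allocation, equal extra effort cancels in the pooled paired difference, which is the natural reading of the planned comparison of plans. The plan does not call for splitting that difference by arm. The gap of bR + bM can be derived from the summaries by plan and arm, but it is not a named comparison. Equal effort also cancels between arms for delivered plans, since every delivered plan is one meant for treatment. All this stands. The cancellation fails when effort differs by method, and the document offers no safeguard against that.

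Nothing in the document shows contours differing by arm, so that route is only a possibility.

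Finally, this is a descriptive, openly unblinded pilot with computer-generated assignment and no decision threshold. That limits the consequences, but a precise paired comparison is still of little use if its two members were not prepared alike.

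**Conclusion.** The point holds as a gap in sequencing. Because arm assignment is not tied to completed planning, the physician and planner can know which of the two required plans will be treated while they shape both. The clearest exposure is secondary objective 2; contour differences could reach further.

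The size is unknown. The pooled shift is −(bR − bM)/2, which is zero for equal effort. It reaches 1.0 point in size for efforts of 3 and 1, and 1.5 points for 3 and 0, against a 90% half-width of 1.16. The gap between the arms' paired means is bR + bM, against 2.33. These yardsticks rest on an assumed SD of 5 points and 25 subjects per arm, and the effort values are illustrative.

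A reader might infer that reordering the steps would remove planning bias altogether. It would remove only the bias from knowing which plan will be treated. A planner who favours one technique still knows which technique is being optimised, and patient-reported xerostomia and quality of life remain open to influence in an open-label trial.

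**What to change.** In Randomization, separate eligibility registration from arm assignment. State that target and parotid contours and both the margin-based and the robust plan are completed and locked before the coordinator requests the arm in RPRS, and that the plan of the assigned arm is then delivered. Locking is for analysis only: any later re-plan is recorded and does not replace the locked pair in objective 2.

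In Statistical Considerations, state which plan feeds which analysis:

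- Objective 2: the locked pair.
- Objective 3, dose received: the delivered plan, including any recorded re-plan.
- Objective 5: say which NTCP value is correlated with change in quality of life.

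The cost is wording and a change in the order of steps. Sample size and stated precision do not change, and two plans per randomized subject are already required. There are two downsides: both plans must be ready before treatment starts, so the second cannot be deferred, and a few subjects who drop out before randomization will have had two plans made. The allowance to consent up to 75 subjects to reach 50 leaves room for such losses.
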